6.5 General Considerations for Statistical Analysis

All statistical tests will be two-sided and a difference resulting in a p-value of less than or equal to 0.05 will be considered statistically significant. All p-values will be rounded to and displayed in four decimals. If a p-value less than 0.0001 occurs it will be shown in tables as <0.0001.

There will be no multiplicity adjustments, or adjustments for multiple comparisons.

Descriptive summaries of variables will be provided where appropriate. For continuous variables, the number of non-missing values (n) and the median, mean, standard deviation, minimum, and maximum will be tabulated by treatment. For categorical variables, the counts and proportions of each value will be tabulated by treatment. Expansion of descriptive table categories within each treatment may occur if such elaborations are thought to be useful.

All collected data will be presented in listings. Data not subject to analysis according to this plan will not appear in any tables or graphs but will be included in the data listings.

Post-hoc exploratory analyses not identified in this SAP may be performed to further examine the study data. These analyses will be clearly identified as such in the final clinical study report. The SAP will not be amended for post-hoc, additional analyses identified after planned analyses are completed. Likewise, the list of planned tables (Section 8.1) is the list of planned tables prospectively defined for the study analyses. Additional tables and figures may be defined to further evaluate study results and the SAP will not be amended to list these additional analysis tables.

6.5.1 Changes in Analysis in Comparison to Study Protocol

The analyses described in this analysis plan are consistent with the intended analyses described in the study protocol. In addition results from the UX001-CL201 study, both the Week 24 and Week 48 analyses, will be utilized as baseline information to explore and compare the various dosing combinations and trends in efficacy parameters, between the UX001-CL201 randomized feeder study and the UX001-CL202 extension study.

6.5.2 Derived Efficacy Variables

Muscle Strength - Hand Held Dynamometry (HHD):

HHD Upper Extremity (UE) composite score is calculated as the sum of the average of the right and left raw scores (as measured in kg) for the following muscle groups: grip, shoulder abductors, elbow flexors and elbow extensors. If a value from the right or left side of an individual muscle group is missing, the missing value will be imputed using the non-missing value from the other side.

HHD Lower Extremity (LE) composite score is calculated as the sum of the average of the right and left raw scores (as measured in kg) for the following muscle groups: hip flexors, hip extensors, hip abductors, hip adductors and knee flexors. Knee extensors will not be included in the calculation of the LE HHD composite score. If a value from the right or left side of an individual muscle group is missing, the missing value will be imputed using the non-missing value from the other side.

Predicted normal HHD values will be derived for the raw strength values from bilateral pinch (tip, key and palmar), grip, shoulder abductors, elbow flexors, elbow extensors, hip flexors, hip extensors, hip abductors, hip adductors, knee flexors and knee extensors collected at baseline using the regression equations generated for the variables. Baseline predicted normal values will be used to derive % of predicted normal values for all future study time points throughout the study.

% of predicted normal HHD values for the individual muscle groups will be calculated as follows: $[(\text{Raw strength value}/\text{Predicted normal strength value}) * 100]$.

Patient Reported Outcomes:

HIBM Functional Activities Scale (HIBM-FAS) Total Score will be calculated as the sum of the Total Scores range from 0 to 100 with higher scores representing greater independence with functional activities. Subscale scores will be calculated for the Mobility, Upper Extremity and Self-Care domains. Mobility subscale scores range from 0 to 40 with higher scores representing greater mobility. Upper Extremity subscale scores range from 0 to 32 with higher scores representing more skilled, independent use of the arms during functional

activity performance. Self-Care subscale scores range from 0 to 28 with higher scores representing greater independence with functional care activities.

6.5.3 Derived Safety, Dosing, and Medication Variables

Non Treatment Emergent Adverse Events (AEs) include all adverse events that stopped the day prior to the start of study medication, started prior to the start of study medication but did not increase in severity or relationship during treatment, or started more than 30 days after the final study medication dosing date. In this study there is no expectation on non-treatment emergent adverse events in any subjects who roll-over from UX0010-CL201. Subjects in the treatment naïve population may have non-treatment emergent adverse events recorded if an event occurs between screening (informed consent) and the first dose of planned study medication (12g.day SA-ER/SA-IR).

Treatment Emergent Adverse Events (TEAE) include all adverse events that start on or after the first dose of study medication, or adverse events that are present prior to the first dose of study medication, but their severity or relationship increases after the first dose of study medication up to and including 30 days after the final study medication dosing date.

Dosing: Number of doses administered will be calculated for each subject by summing the number of doses administered over all visits.

Medications:

Prior medications include all medications that are taken prior to the first dose of study medication date.

Concomitant medications include all medications that are taken on or after the date of first dose of study medication.

6.5.4 Data Handling

Unscheduled or repeated laboratory results will not be analyzed for the summary of continuous values but may be included in any post-hoc laboratory shift tables as follows. Unscheduled tests will be included with the time of the nearest regularly scheduled test. If there is a scheduled laboratory result and one or more unscheduled tests assigned to the same time point, the most conservative test (i.e., a test with low or high results) will be used. Repeated tests will be included only if they reflect abnormal (low or high) results and the corresponding original results are normal.

6.5.5 Handling of Early Termination Visits

Early termination visit data for safety variables will be analyzed at the closest scheduled visit. If the closest visit has valid data, the early termination data will be assigned to the next available visit.

6.5.6 Handling of Missing Values

Partial or Missing Dates

The following conventions will be used to impute missing portions of dates for adverse events and concomitant medications. Note that the imputed values outlined here may not always provide the most conservative date. In those circumstances, the imputed value may be replaced by a date that will lead to a more conservative analysis.

A. Start Dates

- 1) If the year is unknown, then the date will not be imputed and will be assigned a missing value.
- 2) If the month is unknown, then:
 - i) If the year matches the first dose date year, then impute the month and day of the first dose date.
 - ii) Otherwise, assign 'January'
- 3) If the day is unknown, then:
 - i) If the month and year match the first dose date month and year, then impute the day of the first dose date.
 - ii) Otherwise, assign the first day of the month.

B. Stop Dates

- 1) If the year is unknown, then the date will not be imputed and will be assigned a missing value.
- 2) If the month is unknown, then assign 'December.'
- 3) If the day is unknown, then assign the last day of the month.

Imputation of missing endpoint assessments:

Observed cases with data missing at random will be assumed for all planned analyses. If missing endpoint assessments are observed then the last observed value, at the collected time point, will be included in planned analyses.

Following a data review at the 6-month interim analysis and at the completion of the study Ultragenyx Pharmaceutical may at their discretion define an imputation rule if missing data for efficacy assessment and endpoints is believed to be non-random, and has some aspect of systematic error associated with the missing data. If this is determined following data review then a Last Observation Carried Forward (LOCF), or Baseline Observation Carried Forward (BOCF) may be considered for imputation for missing endpoint efficacy data.

Imputation of missing endpoint assessments for HHD measures:

Missing values explained as “**Too Weak**” are to be converted to zero scores for all HHD measures including Grip, Tip Pinch, Key Pinch, Palmar Pinch, Shoulder Abduction, Elbow Flexion, Elbow Extension, Knee Flexion, Knee Extension, Hip Flexion, Hip Extension, Hip Abduction and Hip Adduction.

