5 INTRODUCTION

Sialic Acid-Extended Release (SA-ER, UX001; also termed Ace-ER) is an extended release formulation of sialic acid (SA, also known as N-acetylneurameric acid or NANA) intended as a substrate replacement therapy for GNE myopathies. GNE myopathy, hereditary inclusion body myopathy (HIBM), distal myopathy with rimmed vacuoles (DMRV), and Nonaka disease are all different names of the same disorder, which is caused by a defect in the biosynthetic pathway for SA. For the purposes of this protocol, GNE Myopathy will be used as the term for this disorder.

Patients with GNE Myopathy cannot produce sufficient SA in muscle tissues; consequently glycoproteins and glycolipids in affected patients are not appropriately sialylated.

In humans, GNE Myopathy is a severe progressive myopathy with onset usually in affected patients 18-30 years of age. Initial diagnosis is followed by progressive loss of muscle strength, distal to proximal, which ultimately leads to loss of ambulation in 10-20 years. By replacing SA substrate, sialylation should be restored on key target glycoproteins and glycolipids and should lead to restoration of biochemical function, improved muscle physiology, and improved clinical function.

The scientific rationale for this substrate replacement therapy is primarily based on the nature of the underlying genetic disease and on the work of Malicdan and colleagues, who demonstrated oral SA replacement therapy can be effective in restoring biochemical function with higher levels of sialylation in a relevant HIBM mouse model ([Malicdan et al. 2009](#)). The improved biochemical function in treated mice resulted in reduced or absent HIBM pathology, prevented clinical signs of muscle disease, and improved survival (Malicdan et al. 2009).

SA has a short half-life in the circulation. Rapid clearance makes it difficult to use as a therapeutic replacement substrate in which a steady and constant supply of SA is required for use in glycoprotein and glycolipid synthesis. The SA-ER formulation is expected to provide more stable blood levels of SA without spikes or troughs over the 24 hour cycle in humans when dosed three or four times per day (TID or QID). Continuous exposure is likely an important step in assuring adequate sialylation during peak periods of synthesis, particularly during the night when maximal muscle growth and repair occur.

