6.5.8 Determination of Baseline Values

Multiple baseline values for efficacy endpoints will be considered for the planned analyses. [Figure 1](#) presents an analysis map that highlights the various possible baselines for planned analyses. [Table 3](#) presents a dosing pathway matrix for all subjects enrolled in the study. Each pathway can be associated with a different baseline for analysis summaries and comparisons.

In order to examine the long term trends and changes in SA therapy for those subjects who roll-over from UX001-CL201 additional analyses will also be performed using baseline assessments obtained at the following time points ([Figure 1](#)):

- UX001-CL201 6/6 and 3/3 rollover subjects: UX001-CL201 Week 0 Visit
- UX001-CL201 0/6 and 0/3 rollover subjects: UX001-CL201 Week 24 Visit
- UX001-CL201 0/6 + 6/6 rollover subjects: UX001-CL201 Week 48 Visit
- UX001-CL201 0/3 + 3/3 rollover subjects: UX001-CL201 Week 48 Visit
- UX001-CL201 All rollover subjects: UX001-CL201 Week 48 Visit

- UX001-CL201 All rollover subjects: UX001-CL202 Part I Termination Visit
- UX001-CL202 Treatment Naïve Subjects: UX001-CL202 Part II Screening/Baseline Visit (Week 0: Note that protocol refers to this as week 12 on the T&E schedule.)

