SA-ER	
the change from this score will be compared to the week 24 12g/day SA-ER/SA-IR treatment to assess the impact of the 12g/day SA-ER/SA-IR dose across the combined 3/3+0/3 dose (UX001-CL201 subjects treated with 0/3 or 3/3 SA-ER will be combined for comparison from dosing pathways 2 and 4 from Table 3)
 
A second comparison will be with a 6 minute walk test at Screening of ≥ 200 m (6MWT≥ 200m)

Secondary Analysis: Stability in endpoint over time and dose from Week 0 UX001-CL201 through Week 24 UX001-CL202. (Trend over time)
	
All subjects who roll-over from UX001CL201 will have their week 0 assigned as baseline and the stability from this baseline score will be assessed over time through the week 24 12g/day SA-ER/SA-IR treatment to assess the impact of dose combinations over time. For this analysis the UX001-CL201 subjects treated with 0/6 or 6/6 SA-ER will be combined for analysis from dosing pathways 1 and 3 and subjects treated with 0/3 or 3/3 SA-ER will be combined for analysis from dosing pathways 2 and 4 (Table 3). Each dosing pathway combination will be a separate analysis to assess the trend in endpoint scores over time and dose.
 
A second comparison will be with a 6 minute walk test at Screening of ≥ 200 m (6MWT≥ 200m)

Treatment Naïve Primary Analysis: Week 24 12g/day SA/ER/SA-IR vs. Week 0 Baseline (Week 12 on T&E)
	
Treatment Naïve subjects who enroll in UX001-CL202 will have a primary comparison of their change from baseline assessment for efficacy parameters.

Treatment Naïve Secondary Analysis: Week 24 12g/day SA/ER/SA-IR vs.
	
Treatment Naïve subjects in UX001-CL202

Planned Comparison	Description
Week 0-24 UX001-CL201 Placebo	endpoint data from week 0 to 24 will be compared to the UX001-CL201 Placebo (for those patients with 6MWT >=200m) treated subjects' endpoint data from week 0 to 24 for change from baseline assessments.

Additional comparisons may be defined upon review of the data to examine trends throughout a subject's treatment course through both UX001-CL201 and UX001-CL202, via the dosing pathways identified in [Table 3](#) and [Figure 1](#).

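### For efficacy data believed missing non-randomly, SAP 6.5.6 names only LOCF or BOCF, chosen after review of open-label data; both assume that dropouts stop changing, and no sensitivity analysis tests that assumption

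*SAP*

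**What the plan says.** SAP 6.5.6 sets the default: "Observed cases with data missing at random will be assumed for all planned analyses". It then adds: "If missing endpoint assessments are observed then the last observed value, at the collected time point, will be included in planned analyses". That sentence can mean that whatever was observed is used, or that the last value is carried forward as a matter of course.

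The section then opens an alternative. "Following a data review at the 6-month interim analysis and at the completion of the study", the sponsor "may at their discretion define an imputation rule if missing data for efficacy assessment and endpoints is believed to be non-random". In that event "Last Observation Carried Forward (LOCF), or Baseline Observation Carried Forward (BOCF) may be considered for imputation for missing endpoint efficacy data". No other method is named. The SAP gives no criterion for judging missingness non-random, no rule for choosing between the two methods, and no sensitivity analysis for data missing not at random (MNAR). SAP section 1 states that treatment is not blinded.

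The same section has one fixed rule for informative missingness: an HHD measure missing because the subject was too weak is scored zero.

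On baselines, SAP 6.5.8 says: "Multiple baseline values for efficacy endpoints will be considered for the planned analyses". Table 8 (SAP 6.7.1) uses the Part I Termination Visit for Primary Analysis #1, CL201 Week 48 for #2 and #3, and CL201 Week 0 for the Secondary Analysis. In that last row, "All subjects who roll-over from UX001CL201 will have their week 0 assigned as baseline and the stability from this baseline score" is followed to Month 6 on 12 g/day. Protocol section 5 describes the disease course: "Initial diagnosis is followed by progressive loss of muscle strength, distal to proximal".

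**The concern.** The point concerns subjects who withdraw or miss visits, on every efficacy endpoint. It is not about how inability to perform a test is scored.

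The provision applies when missingness is believed to be informative. In a progressive myopathy the obvious informative mechanism is that subjects who are getting worse leave. The named methods then assume that such subjects have not changed since baseline (BOCF) or have not changed since their last visit (LOCF). The Secondary Analysis asks about stability from baseline, and a BOCF change of exactly zero is the favourable answer to that question.

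The rollover comparisons have no concurrent arm in which the same error could cancel, and Protocol 7.2 concedes that natural progression is hard to separate from treatment effect without a control group. Finally, observed cases, LOCF and BOCF can give different answers, and the choice among them is open until the data have been seen, at Month 6 and again at study end.

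**Working it through.** The documents give no dropout rate, decline rate or bias figure for any endpoint, so there is no plan figure to reproduce. Everything below is in assumed units.

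**Bias formulas.** Let f be the fraction missing at Month 6, c the mean change in completers and d the true mean change in those missing (negative means decline).

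- Truth: (1 − f)c + fd
- Observed-case bias: c − truth = f(c − d)
- BOCF bias: (1 − f)c − truth = −fd
- LOCF bias, linear change, with a share g of the baseline-to-Month-6 interval elapsed at the last visit: −fd(1 − g)

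If d < 0, the BOCF and LOCF biases are both positive, whatever completers do.

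**BOCF against observed cases.** BOCF is the more biased when |d| > |c − d|. With d < 0, that requires c < 0 and |d| > |c|/2. At f = 0.20:

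| c | d | Truth | Observed-case bias | BOCF bias |
|---|---|---|---|---|
| −5 | −10 | −6.0 | +1.0 | +2.0 |
| 0 | −10 | −2.0 | +2.0 | +2.0 |
| +2 | −10 | −0.4 | +2.4 | +2.0 |
| +5 | −10 | +2.0 | +3.0 | +2.0 |
| −5 | −2 | −4.4 | −0.6 | +0.4 |

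**LOCF from Month 3, by baseline.** CL201 lasts 48 weeks and Part I up to 12; Months 3 and 6 are taken as Part II weeks 12 and 24.

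- Part II baseline: g = 12/24 = 1/2
- CL201 Week 48: g = (12 + 12)/(12 + 24) = 24/36 = 2/3
- CL201 Week 0: g = (48 + 12 + 12)/(48 + 12 + 24) = 72/84 = 6/7

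Now let completers decline by 1 unit and dropouts by r. The true decline is T = 1 − f + fr. The share hidden is f(r − 1)/T for observed cases, fr(1 − g)/T for LOCF and fr/T for BOCF. LOCF hides less than observed cases when r(1 − g) < r − 1, that is r > 1/g: above 2, 1.5 and 7/6 ≈ 1.17 for the three baselines.

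| f | r | Observed cases | LOCF, Part II baseline | LOCF, Week 48 | LOCF, Week 0 | BOCF |
|---|---|---|---|---|---|---|
| 5% | 1 | 0% | 2.5% | 1.7% | 0.7% | 5% |
| 5% | 2 | 4.8% | 4.8% | 3.2% | 1.4% | 9.5% |
| 10% | 1 | 0% | 5% | 3.3% | 1.4% | 10% |
| 10% | 2 | 9.1% | 9.1% | 6.1% | 2.6% | 18% |
| 20% | 1 | 0% | 10% | 6.7% | 2.9% | 20% |
| 20% | 2 | 17% | 17% | 11% | 4.8% | 33% |
| 20% | 3 | 29% | 21% | 14% | 6.1% | 43% |

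These columns assume a full 12 weeks in Part I. The note to SAP Figure 1 says some subjects went straight to Part II; for them g is 12/24 from Week 48 and 60/72 from Week 0. HIBM-FAS is not scheduled at Month 3, so LOCF at Month 6 would carry its Part II baseline value.

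**Simulation check.** 300 replicates, n = 46, visits at Months 3 and 6, slope SD 5, subject SD 3, error SD 3, about 21% missing under MNAR. Bias of exchangeable GEE without imputation / LOCF / BOCF, changes measured from the Part II baseline:

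- True mean change −10: +0.93 / +1.64 / +3.17
- True mean change 0: +0.84 / +0.47 / +0.97
- True mean change +4: +0.80 / +0.03 / +0.09

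With dropout depending only on the observed Month 3 value (MAR), the GEE without imputation was still biased by +0.34 to +0.39.

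**The case against.** The strongest reply is that carry-forward need not be worse than doing nothing. The protocol expects improvement (section 7.6.1.1) and its synopsis cites stabilisation of strength in CL201. If completers are stable, BOCF ties with observed cases; if they improve while dropouts decline, BOCF is less biased. LOCF beats observed cases once dropouts decline fast enough, and strongly informative dropout is exactly the trigger. This stands. A reader might infer that BOCF is always worse than no imputation, or that LOCF never helps at moderate r; the documents support neither.

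Three further replies also stand. The wording is permissive, so LOCF and BOCF are the only methods named and not the only ones allowed. The zero score for too-weak HHD measures already penalises one decline-related mechanism, although it needs a recorded reason and covers neither withdrawals nor the other endpoints. And dropout by Month 6 may be low, since rollover subjects had completed 48 weeks and SAP 6.1 adds at least 80% compliance and visit completion.

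It is also tempting to say that BOCF would impute a different value in each Table 8 row, up to 84 weeks old in the Secondary Analysis. That is one possible reading. The SAP does not say which baseline would be carried, and the gap itself is the defect.

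None of this defends leaving the choice until the data are seen. That the ranking depends on unknown completer behaviour is a reason to fix the method beforehand.

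**Conclusion.** The point holds in limited form. For missingness believed non-random, the SAP names only two methods. Each assumes no further change, the choice is discretionary after open-label review, the baseline for BOCF is undefined, and no MNAR sensitivity analysis is planned.

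If dropouts are declining, both methods err towards stability: BOCF by f times their decline, LOCF by f times the part of it that follows the last visit. For 5% to 20% missing and r of 1 to 2, with completers also declining, BOCF hides 5% to 33% of the true decline. That range rests on assumed f and r and, for LOCF, on linear change.

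Whether either method is worse than no imputation cannot be settled from the documents. BOCF is worse only if completers also decline and dropouts decline more than half as fast. Nor is no imputation a safe benchmark, since the observed-case and GEE estimates were biased too.

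This should be changed but is not critical: the provision is contingent, and the study is not powered for comparisons. The estimates are nonetheless its reported efficacy evidence.

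**What to change.** In SAP 6.5.6:

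1. Delete the LOCF/BOCF sentence and the discretion to define a rule after data review.
2. Reword the sentence on the last observed value so that it cannot be read as default LOCF, for example by stating that each observed value is analysed at the visit where it was collected and that missing visits are not filled in.
3. Keep the repeated-measures analysis of all observed visits as the main analysis.
4. Before data review, prespecify one sensitivity analysis for the HHD UE and LE composites and the 6MWT: multiple imputation from all of the subject's earlier CL201 and CL202 visits, first with zero shift (MAR), then with a series of downward shifts after dropout (a delta or tipping-point series).
5. Fix the shift scale in advance. Multiples of the CL201 placebo 24-week change would serve if that change is a decline; the documents do not report it, so a fallback scale is needed.

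The zero-shift run also shows how far the unweighted GEE departs from an MAR-based estimate.

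The cost is SAP wording and a few extra runs on data that the SAP already plans to pool with CL201. The small downside is that the sensitivity estimates may be less favourable and less precise.
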